2.4.1 Definition of Baseline

Unless specified elsewhere, baseline is defined as the last available measurement prior to administration of study drug. For events that occur on the same day as the first administration of study drug (i.e. assessments performed at the Baseline visit), and for which the time of the assessment is not available, the assessment will be classified as pre-treatment, hence baseline. The exception to this rule will be AEs for which the event will be classified as a TEAE.

It should be noted that for the purpose of clinical management, the description of baseline varies in the protocol (e.g. inclusion/exclusion and Drug-Induced Liver Injury Monitoring). For analysis purposes, only the definition above will be used.

2.5 Statistical Assessment of the Study Objectives

The efficacy endpoints will be summarized within the ITT population using descriptive statistics, with the primary endpoint, GGT and total bilirubin, also summarized within the PP

HighTide Biopharma Pty. Ltd.
Protocol HTD1801.PCT013

population. As this study includes one treatment group, the hypotheses, tests, and confidence intervals are all one sample comparisons to baseline. Confidence intervals will be 95% two-sided normal approximation confidence intervals. Testing for the percent change from Baseline to Week 12 in ALP using a t-test will also be performed. Testing will be one sided using a 5% alpha level. No multiplicity adjustment will be used, and the p-values reported for the endpoints will be descriptive in nature.

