#### **12.4.2. Analysis of the Primary Efficacy Endpoint(s)**

Alkaline phosphatase levels, change from baseline, and percent change from baseline will be summarized with descriptive statistics and 95% normal approximation confidence intervals. Testing for the percent change endpoint using a t-test will also be performed. Given the limited sample size (i.e. less than 30 subjects) and the potential for right skewed data the normality assumption may not be fully accurate. Hence, the true alpha level may theoretically not be 5%. As such, these tests will be considered descriptive more than confirmatory.

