2.5.1.2 Analysis Methods

Serum ALP levels, change from baseline, and percent change from baseline will be summarized at each analysis window (see Table 2) using descriptive statistics and 95% confidence intervals. A t-test will also be performed to test for the percent change from baseline to Week 12. This analysis will be based on observed data without imputation. This analysis will be summarized within the ITT and PP population.

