2.5.2 Secondary Analyses

Secondary endpoints, including the secondary ALP endpoints, will be summarized with descriptive statistics by timepoint. These summary measures will include baseline, result at the time point that data is captured, change from baseline, and percent change from baseline as is appropriate for the endpoint. A 95% confidence interval will be produced for changes in laboratory endpoints, within the ITT population.

Endpoints with categorical interpretations (e.g. ELF, GLOBE Score, Pruritus VAS) will additionally be summarized by shift tables for Change from Baseline to Week 12 using the categories listed above.

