2.5.3 Subgroups

The results, change from baseline, and percent change from baseline to week 12 for ALP, total bilirubin, GGT, ALT, AST, and ELF will be performed for the following subgroups:

- ALP at Baseline (above and below median value)
- Total bilirubin at Baseline (above and below median value)

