3.2.2.1 Baseline Laboratory Assessments

Baseline laboratory assessments will be summarized descriptively. This will include:

- ALP
- GGT
- Total Bilirubin
- AST
- ALT
- Albumin
- Platelets
- AMA (Positive, Equivocal, or Negative)
 - For positive values, AMA will also be summarized as a continuous measure
- ANA (Positive, Equivocal, or Negative)
 - For positive values, ANA will also be summarized as a continuous measure

3.2.3 *Concomitant Medications*

Medications with a stop date before the treatment dosing date will be considered prior medications/procedures. Medications with a start or stop date on or after the treatment dosing date will be considered concomitant. All medications marked as ongoing are concomitant.

A medication with an incomplete stop date will be considered concomitant if:

- Month is missing and year is equal to or after the year of treatment dosing date
- Day is missing and year is equal to the year of the treatment dosing date and month is equal to or after the month of the treatment dosing date.

HighTide Biopharma Pty. Ltd.
Protocol HTD1801.PCT013

All concomitant medications will be summarized by preferred terms in descending order of frequency. All medications, including prior and prohibited medications, will be provided in a listing.

3.2.4 *Medical History*

Medical history will be tabulated by system organ class and preferred terms and provided in a listing.

3.2.5 *Clinical Study Treatment and Extent of Exposure*

The total tablets used, duration of treatment, and compliance (see Section 2.2) will be summarized. Average dose received per day, along with the number of subjects with dose interruption or modification will also be summarized.

3.3 *Analysis of Efficacy Endpoints*

3.3.1 *Serum Alkaline Phosphatase*

The serum ALP levels, change from baseline, and percent change from baseline will be summarized with descriptive statistics by timepoint for the ITT and PP populations. The summary measures will include 95% normal distribution confidence intervals of the treatment difference. In addition, a t-test will be performed for the percent change from baseline to Week 12. Subgroup analyses (see Section 2.5.1.2) will be performed for the change from baseline and percent change at Week 12 data.

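### The 95% intervals for mean changes are specified as normal-approximation intervals at n of 30 or fewer; one-sample t intervals should be specified

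*SAP*

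**What the plan says.** SAP 2.5 sets a general rule: "Confidence intervals will be 95% two-sided normal approximation confidence intervals". Its next sentence plans a t-test of the percent change in ALP from Baseline to Week 12. The same section says that "the hypotheses, tests, and confidence intervals are all one sample comparisons to baseline".

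The wording recurs in two places. Protocol 12.4.2 says ALP levels, change and "percent change from baseline will be summarized with descriptive statistics and 95% normal approximation confidence intervals". SAP 3.3.1 says: "The summary measures will include 95% normal distribution confidence intervals of the treatment difference".

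Other places name no method. In SAP 2.5.1.2, which describes the primary analysis, ALP levels, change and "percent change from baseline will be summarized at each analysis window (see Table 2) using descriptive statistics and 95% confidence intervals". SAP 2.5.2 says: "A 95% confidence interval will be produced for changes in laboratory endpoints, within the ITT population". Protocol 12.4.1 asks for two-sided 95% intervals in general, and the protocol synopsis asks for 95% intervals and a one-sample t-test. Neither document gives an interval formula or multiplier, and neither specifies a t-based interval.

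Protocol 12.4.2 adds a caution: "Given the limited sample size (i.e. less than 30 subjects) and the potential for right skewed data the normality assumption may not be fully accurate". It concludes that the true alpha may differ from 5% and that the tests are more descriptive than confirmatory.

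**The concern.** A normal-approximation interval for a mean is ordinarily the mean plus or minus 1.96 standard errors. That multiplier is right when the SD is known or n is large. Here the SD is estimated, enrolment is capped at 30, data are analysed as observed without imputation, and subjects who are off treatment or lack a Week 12 ALP value leave the primary analysis. So n=30 is the most favourable case. The plan allows for the estimated SD in the test and the power calculation, but on a literal reading not in the interval for the same mean.

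The error runs one way, towards overstated precision. SAP 2.5 calls the p-values descriptive, so readers will probably lean on the estimates and intervals when judging whether a placebo-controlled study is warranted. The SAP 2.5 rule is general, so it also governs the intervals for changes in laboratory endpoints. It would apply to the median-split subgroups of SAP 2.5.3 as well (about 15 subjects each if 30 are analysed), although the SAP does not say whether those tables carry intervals.

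**Working it through.** **Inputs.** From SAP 1.5 and protocol 12.2: n=30, mean reduction 15%, SD 25%, one-sided 5% t-test. From SAP 2.8: an interim summary when 15 subjects have reached Week 12. The value n=15 is used for that interim and for roughly one half of a median split; it is not a forecast of the final size.

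**1. The plan's own figure.** The power of the one-sample t-test comes from the noncentral t distribution with n−1 degrees of freedom and noncentrality (15/25)·√n. At n=30 the noncentrality is 0.6 × √30 = 3.286 and the critical value is 1.699, giving power of 94.1%. The stated figure of at least 90% is correct.

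**2. Coverage of the literal interval.** For normal data with an estimated SD, the interval mean ± 1.960·s/√n covers the true mean with probability 2·F(1.960; n−1) − 1, where F is the t distribution function.

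**3. Half-widths.** Half-width = multiplier × 25/√n. The standard error is 25/√30 = 4.564 at n=30 and 25/√15 = 6.455 at n=15.

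| n | t multiplier | Coverage with 1.960 | Half-width, z | Half-width, t | Ratio t/z |
|---|---|---|---|---|---|
| 30 | 2.045 | 94.0% | 8.95 | 9.34 | 1.044 |
| 15 | 2.145 | 93.0% | 12.65 | 13.84 | 1.094 |

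For an observed mean of −15% and SD of 25%, the interval at n=30 is (−23.9, −6.1) with z and (−24.3, −5.7) with t. At n=15 it is (−27.7, −2.3) with z and (−28.8, −1.2) with t.

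**4. Skewed data.** The protocol raises right skew but gives no distribution. As an assumption, take a lognormal Week 12/Baseline ratio with mean 0.85 and SD 0.25 (skewness 0.91). Simulation with 400,000 runs per sample size gives:

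| n | Coverage, z | Coverage, t |
|---|---|---|
| 30 | 93.6% | 94.6% |
| 15 | 92.2% | 94.3% |

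The t interval is closer to 95% but does not reach it.

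**5. Agreement with the one-sided test.** Under the plan's assumptions at n=30, the probability that the one-sided 5% t-test rejects while the two-sided 95% interval includes zero is the power at 1.699 minus the power at the interval's multiplier. This is 94.1% − 90.3% = 3.8% with z, and 94.1% − 88.8% = 5.3% with t.

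**The case against.** The strongest reply is that the defect depends on one reading. With no formula given, the wording may mean only an interval that assumes approximately normal data, and the t interval is one of those. Protocol 12.4.2 gives this some support, because its caution about normality follows both the interval and the t-test. This stands as an uncertainty about what will be programmed. It does not rescue the text: two programmers could produce different intervals from it, and the natural reading is z.

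The effect is also small. At n=30 it is about one point of coverage and 0.39 points of half-width, and the plan makes its p-values descriptive. That is right, and it is why the point is minor. The protocol's own caution concerns skewness and the true alpha of the test; it does not address the interval's multiplier.

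The n=15 figures are less firmly anchored. The interim is to be summarized descriptively, the default summary statistics in SAP 3.1 include no interval, and no interim t-test is listed. Those figures therefore apply only where intervals are actually shown at about that size.

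Finally, a t interval does not improve agreement with the one-sided 5% test. It includes zero slightly more often when the test rejects. This is correct: the case for t rests on coverage, not on matching the test.

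**Conclusion.** The concern holds and is minor. Followed as written, the rule gives intervals that are too narrow for a mean with an estimated SD at these sample sizes. The shortfall from nominal coverage is about 1 point at n=30 and 2 points at n=15. These figures assume a multiplier of 1.96 and normal data; the half-widths also assume the plan's SD of 25%. If the authors meant a t interval, the defect is one of specification only and the remedy is the same. The t interval does not remove the skewness concern that the protocol raises. The estimand, hypothesis, t-test, decision rule and sample size are all unaffected.

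**What to change.** In SAP 2.5 and SAP 3.3.1, and in protocol 12.4.2 if it is amended, specify *one-sample t-based 95% confidence intervals* for mean change and mean percent change in place of the normal-approximation and normal-distribution wording. Limit the sentence to means; any intervals for the responder proportions need their own method.

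As an editorial correction, SAP 3.3.1 should refer to the mean change (or mean percent change) from baseline rather than to a treatment difference, since the study has one arm.

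Optionally, and only as a presentation choice, show a two-sided 90% t interval for the primary endpoint as well. Its upper limit corresponds exactly to the one-sided 5% t-test. Its half-width at n=30 and SD 25% is 1.699 × 4.564, or about 7.76 points. The drawback is that readers would see two intervals for one endpoint.

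The cost is two SAP sentences and one protocol sentence, with 95% intervals about 4% wider at n=30 and 9% wider at n=15. At n=30 under the plan's assumptions, the 95% interval would include zero despite a rejecting test in 5.3% of trials instead of 3.8%.

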**Criteria for Evaluation:**

**Efficacy Evaluation**

Efficacy endpoints will be evaluated with descriptive statistics to include 95% confidence intervals. Testing will be used. For the primary endpoint a one sample t-test against a null hypothesis of no change, will be used with a 5% one-sided alpha level. The safety population will include all treated subjects and the efficacy population will include all treated subjects with at least one post dose ALP assessment. Baseline will be assigned to the last available assessment prior to the start of treatment.

[figure not shown]

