### 12.4. Statistical Analyses

#### 12.4.1. General Approach

Endpoints will be summarized using descriptive statistics. For continuous variables n (number of subjects with data), mean, standard deviation, median, minimum, and maximum will be used. For categorical results the number of subjects and the percent of subjects per category will be summarized. Confidence intervals will be generally reported using 95% two-sided confidence intervals. When testing is used p-values with four decimal places will be reported; no adjustment for multiplicity will be conducted.

Missing data will not be imputed for the efficacy analyses. Missing dates for adverse events and concomitant medication will be imputed to allow these items to be summarized as on or off treatment.

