#### **12.4.3. Analysis of the Secondary Endpoint(s)**

The secondary endpoints including the secondary ALP endpoints will be summarized using descriptive statistics. Summary statistics at each timepoint that data is captured will be provided for the result as well as the change from baseline, when change from baseline is applicable. Confidence intervals will be produced for changes in serum bilirubin and change in gamma-glutamyl transferase.

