The proportion of subjects who have $\geq 20\%$ and the proportion with a $\geq 40\%$ decrease in ALP from Baseline will be summarized at each timepoint with Week 12 being the study specified timepoint. Additionally, the proportion of subjects who normalize ALP will be summarized by timepoint.

3.3.2 *Secondary Endpoints*

Tables for the secondary endpoints, see below, will be summarized for the respective laboratory values and the change from baseline results at each timepoint. Total bilirubin and GGT will be summarized within the ITT and PP populations. Subgroup analyses for specified laboratory parameters (see section 2.5.2) will be performed for the change from baseline and percent change at Week 12. Central and local lab data will be used for the efficacy analyses.

- Total bilirubin
- GGT
- ALT
- AST
- Total cholesterol

- LDL
- Triglyceride
- Fibrinogen
- CRP
- Haptoglobin
- ELF
- Immunoglobulins (IgM and IgG)

3.3.3 *UDCA Use*

A plot of average percent change in ALP at each timepoint through Week 12 for groups defined by the ratio of current to prior dose of UDCA. The ratio groups displayed in the plot will be <90%, 90% to 110%, and >110%. Separate subject level plots will also be presented for each ratio group through Week 12.

3.3.4 *ELF Score*

The number of subjects within ELF score interpretations will be presented at Week 12 as well as the shift within categories for change from baseline to week 12. Summary statistics at Week 12 will also be presented.

3.3.5 *GLOBE Score*

The number of subjects within GLOBE score interpretations will be presented along with the Fibrosis Score interpretations. Change in GLOBE score from baseline will be summarized using descriptive statistics at Week 6 and Week 12. A listing of the GLOBE score will also be produced and summarized by duration of UDCA exposure.

Survival risk (%) for 5, 10, and 15 years will be summarized using descriptive statistics at Week 12 for the GLOBE Scores.

3.4 *Analysis of Safety Endpoints*

Safety Endpoints (Adverse Events, Clinical Laboratory Results, Vital Signs) will be presented at the scheduled timepoints as outlined in Table 1, with further detail in the protocol.

3.4.1 *Adverse Events*

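### No interval method suited to proportions is named for the three ALP responder endpoints, and the one method named behaves badly at low response rates with 30 or fewer subjects

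*SAP*

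**What the plan says.** **Where intervals are promised in general terms.** The protocol synopsis (Efficacy Evaluation) says: "Efficacy endpoints will be evaluated with descriptive statistics to include 95% confidence intervals". Protocol 12.4.1 gives the level but no method: "Confidence intervals will be generally reported using 95% two-sided confidence intervals". SAP 2.5 gives the method without limiting it to a type of endpoint: "Confidence intervals will be 95% two-sided normal approximation confidence intervals".

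**Where intervals are assigned to particular endpoints.** Each of these passages concerns continuous measures.

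- Protocol 12.4.2, for ALP level, change and percent change: "summarized with descriptive statistics and 95% normal approximation confidence intervals".
- Protocol 12.4.3, for secondary endpoints: "Confidence intervals will be produced for changes in serum bilirubin and change in gamma-glutamyl transferase".
- SAP 2.5.2: "A 95% confidence interval will be produced for changes in laboratory endpoints, within the ITT population".
- SAP 3.3.1, for ALP level, change and percent change: "The summary measures will include 95% normal distribution confidence intervals of the treatment difference".

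**What is said of the proportions.** SAP 2.3 lists three of them as ALP secondary efficacy endpoints: decrease of at least 20%, decrease of at least 40%, and normalisation. SAP 3.3.1 says that the two decrease endpoints are to be summarised by timepoint, and then: "Additionally, the proportion of subjects who normalize ALP will be summarized by timepoint". It mentions no interval there. Neither document names a score or exact method anywhere.

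**The concern.** A programmer who reads the synopsis together with SAP 2.5 has a promise of intervals for efficacy endpoints and one method for producing them. For a proportion, a normal-approximation interval is the Wald interval. It is known to fail when the expected number of responders is small, and that is plausible here for at least one endpoint. Entry requires ALP of at least 1.5 times the upper limit of normal (ULN), so a subject at the threshold must fall by a third to normalise, against a planned mean fall of 15%.

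At stake is how a low count is reported. If nobody normalised, the output would read 0% with an interval of 0% to 0%, which claims certainty from at most 30 subjects. The same ALP secondary endpoints are summarised when 15 subjects reach Week 12 (SAP 2.8), where the behaviour at low rates is worse.

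**Working it through.** **Inputs.** n = 30, mean percent reduction 15%, SD 25%, one-sided 5% alpha (Protocol 12.2, SAP 1.5). Interim at 15 subjects (SAP 2.8). Entry ALP at least 1.5 × ULN (Protocol 5.1). The documents give no expected responder or normalisation rate, so the true rates below are a range or follow from a stated assumption.

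**Step 1: the plan's own figure.** One-sample t-test power with noncentrality (15/25) × √30 = 3.29 and 29 degrees of freedom is 94.1%. The stated bound of at least 90% is reproduced, and nothing below affects it.

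**Step 2: the intervals.** The Wald interval is p̂ ± 1.96 × √(p̂(1 − p̂)/n). At n = 30:

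| Responders | Wald | Wilson | Clopper-Pearson |
|---|---|---|---|
| 0 | 0% to 0% | 0% to 11.3% | 0% to 11.6% |
| 1 | −3.1% to 9.8% | 0.6% to 16.7% | 0.1% to 17.2% |
| 2 | −2.3% to 15.6% | 1.8% to 21.3% | 0.8% to 22.1% |
| 3 | −0.7% to 20.7% | 3.5% to 25.6% | 2.1% to 26.5% |
| 4 | 1.2% to 25.5% | 5.3% to 29.7% | 3.8% to 30.7% |

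The exact upper limit for 0/30 is 1 − 0.025^(1/30) = 11.6%. For 0/15 it is 1 − 0.025^(1/15) = 21.8%. Zero width needs 0 (or all) responders. A negative lower limit needs 1 to 3, at both n = 15 and n = 30.

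**Step 3: actual coverage.** Coverage is the binomial probability of the counts whose Wald interval contains the true rate p. At n = 30:

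- p = 5%: counts 1 to 5 cover. Coverage = 1 − P(X = 0) − P(X ≥ 6) = 1 − 0.2146 − 0.0033 = 78.2%.
- p = 10%: counts 2 to 7 cover. Coverage = 1 − 0.1837 − 0.0078 = 80.9%.
- p = 15.9%: counts 3 to 9 cover. Coverage = 1 − 0.1242 − 0.0142 = 86.2%.

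Wilson coverage at the same rates is 93.9%, 97.4% and 95.6%. Wald coverage is not monotone in p: at n = 30 it is 45.4% at 2%, 88.3% at 7%, 94.2% at 15% and 94.6% at 20%. It is below 85% only for true rates up to about 11%. At n = 15 it is 53.6% at 5% and 79.2% at 10%.

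**Step 4: which endpoints sit at low rates.** Assume percent change is normal with the planning mean −15 and SD 25.

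- Fall of at least 20%: Φ((−20 + 15)/25) = Φ(−0.2) = 42%. Wald coverage is 93.7% at n = 30 and 88% at n = 15.
- Fall of at least 40%: Φ((−40 + 15)/25) = Φ(−1) = 15.9%. Wald coverage is 86.2% at n = 30.
- Normalisation from 1.5, 2 or 3 × ULN needs falls of 33.3%, 50% or 66.7%: Φ(−0.73) = 23%, Φ(−1.4) = 8%, Φ(−2.07) = 2%. Only 1.5 is taken from the documents (the entry threshold); 2 and 3 are illustrations.

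If the true normalisation rate were 5%, 0/30 would occur 21% of the time and 0 to 3 responders 94% of the time, so a zero-width or negative-limit interval would be the usual output.

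**The case against.** The strongest reply is that the detailed text plans no interval for any proportion. Just before the method sentence, SAP 2.5 describes its intervals as one-sample comparisons with baseline, and a responder proportion has no baseline value. Every passage that assigns intervals endpoint by endpoint attaches them to levels or changes. The general conventions (Protocol 12.4.1, SAP 3.1) define categorical summaries as counts and percentages only. On that reading the synopsis is merely looser than the SAP. This largely stands: a reader might infer that the SAP prescribes Wald intervals for the proportions, and the documents do not say so. What remains is that either the synopsis promise is unmet for three listed efficacy endpoints, or the only stated method suits them poorly.

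A reader might also infer that coverage near 80% applies to all three proportions. It does not. It holds near true rates of 5% and 10% at n = 30; the 20% endpoint is close to nominal there under the planning assumptions. Those implied rates depend on normality, which Protocol 12.4.2 itself doubts.

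Nor do the documents make these proportions the basis for proceeding to a placebo-controlled study. Protocol 12.4.7 and SAP 2.8 tie early stopping of enrolment to the effect on serum ALP, and set no threshold on a proportion or an interval. Counts will be reported, so a reader would see 0 of 30.

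**Conclusion.** The point holds as a gap in specification with a conditional consequence. The documents do not settle whether the three ALP proportions receive intervals, and no method suited to proportions is named. If the named method is used and response rates are low, the intervals are degenerate or extend below zero, and they under-cover by roughly 9 to 17 percentage points at n = 30 for true rates of 5%, 10% and 15.9% (95 − 86.2 = 8.8; 95 − 78.2 = 16.8). The shortfall is larger at rarer rates.

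Normalisation is the endpoint most exposed, the 40% endpoint less so, and the 20% endpoint hardly at all at n = 30. The expected rates rest on assumed normality and, for normalisation, on assumed baseline multiples.

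Importance is minor. The endpoints are secondary, untested and descriptive, and the primary t-test is unaffected. Because no test is planned for them, an interval would be the main statement of their uncertainty, so it is worth getting right.

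**What to change.** In SAP 2.5, limit the normal-approximation sentence to mean changes, and add that the Week 12 ALP proportions (decrease of at least 20%, decrease of at least 40%, normalisation) will be reported with Wilson or Clopper-Pearson 95% intervals, naming one of the two. Repeat this in SAP 3.3.1, so that the table specification agrees with the synopsis. The change need not extend to the additional analyses in SAP 2.3 or to the liver-monitoring threshold summary, which are not protocol endpoints.

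The cost is a short text change in two sections of the SAP. It needs no new data and no design change. Intervals near 0% become somewhat wider: for 1 of 30, the upper limit moves from 9.8% to 16.7% (Wilson) or 17.2% (Clopper-Pearson). Clopper-Pearson is the more conservative choice, with coverage of 98.4% and 99.2% at true rates of 5% and 10%, against 93.9% and 97.4% for Wilson.
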